11.2 CRITERIA FOR DISCONTINUATION OF STUDY PARTICIPATION

1. Low compliance
2. New acute suicidality
3. Deterioration by more than 25% on MADRS
4. In case of unacceptable side effects such as the development of manic state, impulse control disorder, or symptoms of heart failure
5. Pregnancy
6. The research subject may terminate his/her participation in the study at any time without incurring any consequences for his/her further treatment.

Investigators may at any time discontinue a research subject's participation in the study due to, for example, unacceptable side effects, deteriorating mental health status, or non-compliance with the procedures in the study protocol (see study adherence section 12.8).

If research subjects discontinue prematurely, a plan will be drawn up for the discontinuation of pramipexole (tapering schedule). This is done according to recommendations in FASS but can be adapted individually if needed (e.g. withdrawal side effects that lead to slower joint progression).

12 STUDY DESIGN

Visit	Screening	Baseline (last two weeks after Screening)	v1, v3, v5, v7, v9 +/- 2 days	V2, V4, V6, V8 +/- 2 day	v10 (termina tion) +/- 2 day	Follow-up during Tapering (v14) +/- 2 days
Informed consent	X					
Anamnesis	X					
MINI	X					
SUAS	X					
SHAPS		X		X	X	
MAP-SR		X		X	X	
GAD-7		X		X	X	
YMRS		X		X	X	
PGSI	X	X		X	X	
Insomnia Severity Index		X		X	X	
Fatigue Severity Scale		X		X	X	
Apathy Evaluation Scale		X		X	X	
Physical examination	X					
Blood pressure control	X			X	X	
Incl./exclusion criteria	X	X				
Blood tests β-hCG (if female of childbearing potential), eGFR, liver status, Hb.	X				X	
Inflammation tests (CRP, leukocytes, IL-6, TNF-alpha)		X			X	
fMRI (sub-study)		(X)			(X)	
Distribution of study product		X		X	(X)	
MADRS	X	X		X	X	
DARS	X	X		X	X	
Telephone contact			X			X
Incidents (AEs)			X	X	X	X

12.1 RECRUITMENT/SCREENING

Physicians and nursing staff at general psychiatric clinics and inpatient wards (Region Skåne) are informed about the study and its inclusion criteria. Patients are asked to participate in the study. We will also advertise research subjects. Contact is made with the physician responsible for the patient (PAL) to ensure that he or she is prepared to possibly take responsibility for tapering or continued treatment with pramipexole after the end of the study (tapering can also take place within the framework of the study). The research subject is contacted for booking of *screening* visits that take place at the research clinic. During the visit, anamnesis is recapitulated, somatic diseases, ongoing drug treatment and psychiatric status is performed. Clinical suicide risk assessment is based on psychiatric status and with the help of *Suicide Assessment Scale (SUAS)*²⁷. In *Mini International Neuropsychiatric Interview (MINI)*²⁸ is done for the purpose of confirming (or rediagnosing) psychiatric diagnoses. Assessment of symptoms is made using the MADRS rating scales²⁹ (depression symptoms) and DARS³⁰ (anhedonia symptoms). Inclusion and exclusion criteria are systematically assessed and the research subject's initials and year of birth as well as the time of *screening*-visits are documented (*screening*-log). Each research subject is identified by a unique number (enrollment log). The research subject must provide a blood sample in connection with the screening visit (β -hCG [if woman of childbearing potential], eGFR, liver status and Hb). These samples must be checked before a baseline visit can be considered. The research subject will also provide blood samples in connection with the baseline visit for analysis of inflammatory markers (CRP, leukocytes, IL-6 and TNF-alpha). No biological samples are collected for later analysis. A clinical control of status and pulmonary status is performed (including anamnestic questions with a focus on heart disease and auscultation of COR/pulm and blood pressure), and a note is written in the research subject's medical record. If the research subject is to participate in an fMRI examination, information about the procedure is distributed. Before the *baseline* visit has been made, it is ensured that the blood test results (of hCG, eGFR, liver status and Hb) are assessed and cancel the visit if these are abnormal (referral to the appropriate health care provider for further investigation/action is then sent if necessary).

12.2 PROCESS FOR OBTAINING INFORMED CONSENT

During the *screening* visit, before reviewing the medical history and inclusion and exclusion criteria, the research subject is informed orally about what it means to be part of the study. The information is then distributed on paper together with a signature form. The research subject is then allowed to read through the information in peace and quiet. The form is then signed and in connection with that, the research subject is again informed that it is possible to discontinue the study throughout the study and that they will then receive help with tapering off pramipexole if needed. Ethical aspects of processes that deviate from normal practice/statutory statutes are described in section 20.

12.3 PRIOR TO STUDY TREATMENT - *BASELINE*

In connection with the baseline visit, blood samples are taken for TNF-alpha, IL-6, CRP and Leukocytes. New estimation with MADRS and DARS is performed and with *Generalized Anxiety Disorder 7 scale* (GAD-7; anxiety symptoms), *Insomnia Severity Index*³¹ (sleep problems), Fatigue Severity Scale³² (fatigue symptoms), *Apathy Evaluation Scale*³³ (AES; apathy), Snaith-Hamilton Pleasure Scale³⁴ (SHAPS) The Motivation and Pleasure Scale (MAP-SR)³⁵ (anhedonia symptoms), and with the Young Mania Rating Scale (YMRS) (manic symptoms)³⁶. Study drugs will be dispensed, and the study participant will begin treatment during the day (before bedtime) with the up-titration schedule described in section 13.3. A diary for dosage is handed out and the patient is instructed to bring this filled in at the next visit. On the same day as the start of pramipexole treatment, an fMRI examination is performed for the research subjects as Participating in Sub-studies. On X-ray department Ensures that there are no contraindications

to fMRI (no magnetic implants, normal renal value). Execution of fMRI examination is described in section 26.1. The research subject spends approximately one hour in the scanner and receives compensation for participation after the survey (see section 20.5).

12.4 ALLOCATION OF TREATMENT

Study participants are assigned a generic version of pramipexole (Pramipexole Orion, see section 13).

12.5 DURING TREATMENT

Every two weeks during the study, the research subject is called to the research clinic to discuss up-titration and side effects as well as new assessment with MADRS and DARS. Blood pressure control is performed. A review of the dosing diary and assessment of compliance is sufficient for continued participation in the study (number of days of treatment completed, correct dosage, possible change of other antidepressant/mood stabilizing drugs). Every two weeks (between physical visits), telephone contact is made with the research subjects to check the up-titration status and any side effects. In case side effects develop between Visits/telephone contacts the research subject is asked to report this directly. The strategy if side effects occur is to go back to the last tolerable dose and wait seven days before re-attempting to increase (see section 13 for details).

12.6 FINAL VISIT

After ten weeks, a final visit is made. New blood samples of inflammation markers are taken in the morning, and a new fMRI scan is performed on the research subjects participating in the substudy. The highest tolerable dose of pramipexole is noted and new estimation with MADRS and DARS is performed. A tapering schedule is drawn up if necessary.

12.7 IN CASE OF EARLY DISCONTINUATION OF STUDY PARTICIPATION

If the research subject wishes to discontinue the study voluntarily or if it is deemed inappropriate to continue (e.g. lack of *compliance*, unacceptable side effects, deterioration of mental health), the research subject is offered a new visit or telephone contact to, among other things, establish a de-escalation schedule. Too rapid discontinuation of pramipexole increases the risk of withdrawal side effects in the form of e.g. apathy, anxiety, depression, fatigue, sweating and pain. When tapering becomes relevant, this will be done according to the structure of FASS (vg, see 13.3 below). The research subject is asked if the collected data (from fMRI examination) can continue to be stored and analyzed. Premature discontinuation is recorded, and significant and/or serious incidents are followed up after four weeks until the investigator deems it completed or after two attempts of contact without result.

12.8 COMPLIANCE

The requirement for study compliance is that the research subject participates in screening, *baseline* and final visits and taking pramipexole over 75% of the days prescribed regardless of dosage. Every other week, the research subject is questioned about the number of tablets taken (control of dosage diary). Investigators may also terminate the subject's participation if the intake of pramipexole is exceeded.

13 STUDY DRUG

13.1 INVESTIGATIONAL MEDICINAL PRODUCTS

In the study, the investigational medicine contains the active substance pramipexole. In Sweden, it was previously marketed under the name Sifrol but is now available in several generic versions. The dosage of pramipexole can be stated either as a base or as salt. In FASS, it is first and foremost the dosage as a base that is stated and the corresponding concentration in salt is given in parentheses. This protocol specifies dosage in salt form to be consistent with dosage indicated in the literature and abroad. In the diary and patient information for study participants, the dose is stated in base, as is stated on the medicine package and in the FASS.

Pramipexole is approved in the EU and is indicated as a symptomatic treatment of idiopathic Parkinson's disease, alone (without levodopa) or in combination with levodopa, in the maximum dose of 4.5 mg of salt. Pramipexole is also indicated as a symptomatic treatment of moderately to severely idiopathic restless legs syndrome in doses up to 0.75 mg of salt. Both apply to adults and not to children.

Pramipexole has a purely antidepressant effect (in addition to the effect on the underlying disease) in patients with Parkinson's disease, according to clinical studies. It has also been shown to reduce anhedonia symptoms in these patients³⁷. However, pramipexole has no approved indication for the treatment of mood disorders. In this study, the research subjects will reach a maximum dose of 4.5 mg of salt/day that is already approved for the treatment of Parkinson's disease.

Common Side Effects According to FASS (Indication Parkinson's Disease):

Very common (≥ 1/10): Somnolence, Dizziness, Dyskinesia and nausea.

Common (≥ 1/100, < 1/10): Insomnia, Hallucinations, Abnormal dreams, Confusion, Behavioral symptoms of disturbed impulse control and compulsive behavior, Headache, Visual impairment incl. diplopia, blurred vision and impaired visual acuity, Hypotension, Constipation, Vomiting, Fatigue, Peripheral oedema, Weight loss incl. decreased appetite.

13.2. HANDLING AND LABELLING OF INVESTIGATIONAL MEDICINAL PRODUCTS

The investigational medicine is ordered from pharmacies that also carry out labelling. The medicine is then distributed in connection with the visits. In the study, prolonged-release tablets manufactured by Orion Pharma are used in strengths (salt) 0.375 mg, 0.75 mg, 1.5 mg, and 3 mg.

13.2.1 Labelling of Investigational Medicinal Products

The specific labelling of the investigational drug will take place in accordance with the Medical Products Agency's regulations.

13.2.2 Traceability of Investigational Medicinal Products

We use the drug accountability log and patients note the intake of drugs in the diary. Leftover medicines are returned to pharmacies.

13.2.3 Storage of Investigational Medicinal Products

Storage takes place in a locked cabinet, room temperature, at a nurse's office at the research unit.

13.3 DOSAGE AND ADMINISTRATION OF MEDICINAL PRODUCTS

The study is based on the hypothesis that it is necessary to reach a high daily dose of pramipexole as possible to achieve the expected effects (reduced anhedonia) reported in other studies^{16, 19}. Thus, in the event of intolerable side effects, one will return to a lower dosage and make a new attempt at a dose

increase at a later time (side effects such as nausea, headache, etc. usually disappear after a week).

The study uses prolonged-release tablets that are taken once a day. In a phase I study, the minimum and maximum plasma concentrations and exposure were equivalent to the same daily dose of pramipexole prolonged-release tablets given once daily and pramipexole tablets given three times daily. Once daily administration of pramipexole prolonged-release tablets cause fewer fluctuations in pramipexole plasma concentrations over 24 hours compared to three times daily administration of pramipexole immediate-release tablets.

Up titration takes place according to FASS, that is:

Week 1: 1 tablet in strength 0.375mg for 7 days - daily dose 0.375mg

Week 2: 1 tablet in strength 0.75mg for 7 days - daily dose 0.75mg

Week 3: 1 tablet in strength 1.5 mg for 7 days - daily dose 1.5 mg

Week 4: 1 tablet in strength 1.5 mg and 1 tablet in strength 0.75 mg for 7 days - daily dose 2.25 mg

Week 5: 1 tablet in strength 3 mg for 7 days - daily dose 3 mg

After that, we will make a further increase of 0.75 mg every seven days up to a maximum dosage of 4.5 mg, depending on treatment response and side effects (see below).

The tablets are usually taken at night if the research subject does not have sleep problems. If non-tolerable side effects occur in connection with an increase in dose, the research subject is encouraged to notify this and return to the dosage that did not cause side effects. After that, wait another seven days before a new attempt at dose increase occurs. This is done on a maximum of two occasions before giving up attempts to reach a higher dosage (treatment continues with the lower dosage if possible). An exception to this strategy is if the study participant experiences side effects in the form of impulse control disorder (e.g. pathological gambling addiction or compulsive buying behavior), manic state, or symptoms of heart failure. If such a situation arise, pramipexole will be tapered off and discontinued. Study participants will be assessed with YMRS at baseline, week 2, week 4, week 6, week 8 as well as at week 10 to evaluate any manic symptoms.

The total duration of treatment is ten weeks before an evaluation of efficacy is made and a decision is made on continued treatment or discontinuation (referral is sent to PAL, which is responsible for continued treatment with pramipexole). If the research subject during the study shows a 50% decrease on MADRS or a 50% increase on DARS (=response), further dose increase is stopped, and the research subject then remains on this dose for the rest of the study. Control of *compliance* This is done by asking the research subject to bring the remaining tablets (and dosage diary) to the evaluation visits every two weeks for control counting of the number of tablets.

Pramipexole treatment must not be stopped abruptly due to the risk of dopamine *agonist withdrawal syndrome* (DAWS) with symptoms such as depression, anhedonia, apathy, anxiety, sleep disturbances, and others. The study participant is carefully informed about this. If discontinuation of the drug becomes necessary, this will be done gradually as instructed in FASS: The pramipexole dose is gradually reduced by 0.75 mg of salt per day until the daily dose is reduced to 0.75 mg of salt. The dose should then be reduced by 0.375 mg of salt per day. The patient is instructed to report any withdrawal side effects and then the dose reduction can be individualized to counter them.

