Method description	
Patients will be recruited from outpatient psychiatric clinics or inpatient wards. Those who meet the inclusion criteria and none of the exclusion criteria will, at the screening visit, undergo a baseline assessment including self-report rating scales and blood sampling for inflammatory markers (CRP, IL-6, TNF-alpha, white blood cells).
 
Participants who also consent to the substudy will undergo an fMRI examination of the brain's reward system (MID task). Thereafter, study treatment will begin according to the protocol, with dose escalation once weekly until treatment effect, maximum dose, or intolerable side effects occur. In the event of intolerable side effects, the participant will return to the last tolerable dose. A new attempt at dose escalation may be made after seven days, up to a maximum of two attempts. If serious adverse events occur, the medication will be tapered off.
 
After ten weeks of pramipexole treatment, a final visit will be conducted including new assessment with self-rating scales and blood samples as at baseline visits (including new fMRI examination for those participating in the substudy).

Financing	
The study is financed by funds from ALF, the Söderström-Königska Foundation, SUS Donations and Foundation and the Royal Physiographic Society in Lund.

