14.2.3. Tolerability variables

Adverse reactions to pramipexole treatment are collected in connection with visits (biweekly physical visit and biweekly telephone contact). If adverse reactions develop between two visits, the research subject is asked to report this, and the strategy is usually to go back to the last tolerable dose and wait 7 days before making a new attempt at elevation (see section 13.3 for details).

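### Section 13.3's step-back-and-retry default omits new hallucinations, delusions and confusion from its exceptions, so it permits up to two re-escalations after a non-serious but non-tolerable event of that kind

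*Combined protocol and SAP*

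**What the plan says.** Section 13.3 sets out the dosing strategy. On intolerable effects, "one will return to a lower dosage and make a new attempt at a dose" increase later; the reason given is that effects like nausea and headache tend to settle within a week. The operative rule is a return to the dose that caused no side effects, a seven-day wait and a new increase: "This is done on a maximum of two occasions before giving up attempts to reach a higher dosage".

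The exemption follows: "An exception to this strategy is if the study participant experiences side effects in the form of impulse control disorder", manic state, or symptoms of heart failure. In these three cases pramipexole is tapered and stopped. The only e.g. in that sentence sits inside the impulse-control item, so the list of three is closed.

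Other sections describe the same strategy with different force:
- Section 12.5: "The strategy if side effects occur is to go back to the last tolerable dose and wait seven days before re-attempting to increase", with a reference to section 13 for details.
- Section 14.2.3: "the strategy is usually to go back to the last tolerable dose and wait 7 days before making a new attempt at elevation", with a reference to 13.3.
- Synopsis, method description: "A new attempt at dose escalation may be made after seven days, up to a maximum of two attempts". It adds: "If serious adverse events occur, the medication will be tapered off".
- Section 13.3, on increases above 3 mg: these are made "depending on treatment response and side effects".

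Section 11.2 item 4 makes unacceptable side effects a reason for discontinuation and gives the same three events, but only as examples. Section 11.2 also lets the investigator stop a participant at any time, including for worsening mental state.

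**The concern.** Section 8 lists hallucinations, delusions, confusion, mania and disturbed impulse control together as possible severe reactions. Mania and impulse control became mandatory-taper events in 13.3; the other three did not. The stated reason for retrying, that nausea and headache pass within a week, does not speak to psychotic or confusional effects.

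This is a matter of participant safety, not inference. Staff who follow 13.3 as written could raise the dose again, to the level that preceded a non-tolerable hallucination or confusional state, once or twice. During treatment the protocol assigns YMRS to manic symptoms and PGSI plus specific questions to impulse control. It assigns no instrument to psychotic or confusional effects, which rely on the general incident question at each weekly contact.

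**Working it through.** The plan states no design figure on this point apart from the cap on retries. That cap is two in both 13.3 and the synopsis, so the two agree.

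**Step 1: is the effect exempted anywhere?**

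| Source | Bearing on a non-serious, non-tolerable new hallucination, delusion or confusion |
|---|---|
| 13.3 exemption | Three named events; not these |
| 11.2 item 4 | Open list; applies if the effect is judged unacceptable, but these events are not named |
| 11.2, investigator discretion | May stop; not obliged to |
| Synopsis, serious events | Taper, but only if serious (15.1 item 6 widens this to other medically significant events) |
| Synopsis and 14.2.3, retry wording | Retry may, or usually does, follow; not barred |
| 11.1.2 items 4 and 7 | Psychotic disorder and dementia excluded at entry; silent on effects emerging on treatment |

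No row bars re-escalation.

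**Step 2: do the risk statements explain the omission?** Section 8 ties these reactions to the elderly after long-term treatment and expects lower risk here. The same sentence applies those qualifiers to mania and impulse control, so they cannot explain why only the latter two are exempted. Section 13.1 puts hallucinations, confusion and impulse-control symptoms in the same frequency class, common (at least 1/100, below 1/10), for Parkinson's disease. Section 8 also says that doses above 4.5 mg make neuropsychiatric effects more likely, so the protocol treats them as dose-related.

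**Step 3: can both retries occur within the ten weeks?** Dose step k (k = 2 to 7, 0.75 to 4.5 mg) starts on day 7(k−1)+1 of the 13.3 schedule. Assume that the effect appears on day d (1 to 7) of each exposure, and that step-back starts the next day and lasts seven days.

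- First retry starts on day 7(k−1)+d+8.
- Second retry starts on day 7(k−1)+2d+15.

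| Dose, mg | First day | Second retry, d = 1 | Second retry, d = 7 |
|---|---|---|---|
| 0.75 | 8 | 24 | 36 |
| 1.5 | 15 | 31 | 43 |
| 2.25 | 22 | 38 | 50 |
| 3 | 29 | 45 | 57 |
| 3.75 | 36 | 52 | 64 |
| 4.5 | 43 | 59 | 71 |

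Of 6 × 7 = 42 combinations, the first retry starts by day 70 in all 42 and the second in 41. The exception is 4.5 mg with d = 7 (day 71). So the calendar does not prevent a second retry. This says nothing about how often one would happen.

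**Step 4: frequency.** The documents give no rate for the affected events in this population. If the Parkinson's class of 1% to 10% is assumed per participant, the chance of at least one case among 15 is 1 − 0.99^15 = 14% to 1 − 0.90^15 = 79%. That counts serious and tolerable cases as well, so it overstates the affected subset and is not used as the size of the point.

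**The case against.** The strongest reply is that the protocol already leaves the decision with a physician. Section 12.5 calls participants in to discuss titration and side effects, and 15.5 has incidents reported between visits so that dose changes can be discussed. A new non-tolerable psychotic symptom would ordinarily be judged unacceptable under 11.2 item 4 or count as worsening mental state. Serious events are tapered. The rationale in 13.3 points to transient somatic effects, so staff may not think of retrying after a hallucination at all. A participant who has reached the 50% response criterion gets no further increase anyway.

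Most of this stands, and it limits the weight of the point. It does not remove it: the same discretion exists for mania and impulse control, and the protocol still made taper explicit for those.

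A reader might infer that 13.3 orders rechallenge, or that it contradicts 11.2. The documents support neither. The wording in the synopsis and 14.2.3 makes retry a default, and a default dosing strategy can stand beside a discretionary stopping rule. A reader might also take 41 of 42 as a measure of risk. It is calendar arithmetic that assumes the effect recurs on the same day of each exposure and that a retry is chosen each time.

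**Conclusion.** The point holds as a gap in a safety rule. For a non-serious but non-tolerable new hallucination, delusion or confusional state tied to a dose increase, 13.3 permits up to two re-escalations and nothing in the protocol bars them. The maximum exposure is two retries per affected participant. I judge the event unlikely, given the entry exclusions, weekly contact and physician discretion, but the documents provide no rate to confirm that. No estimate, test or sample-size figure changes.

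It might seem to follow that every clinically significant psychotic or confusional symptom should force a taper. The documents do not support going that far. The gap concerns renewed escalation after a non-tolerable effect. A moderate symptom on the 15.3 scale may be tolerable. Section 13.3 already provides for staying on a lower dose once retries are given up. Sections 12.7 and 13.3 also warn that withdrawal itself can bring depression, apathy and anxiety.

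**What to change.** Add to 13.3: after non-tolerable new hallucinations, delusions or confusion there is no re-escalation. The participant returns to the last tolerated dose, and pramipexole is tapered on the existing 13.3 schedule if the symptom persists or is judged unacceptable. Add these events to the examples in 11.2 item 4. State that mild or tolerable symptoms do not trigger the rule.

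The cost is one added rule in 13.3 and one phrase in 11.2, with an amendment under 20.1 possibly needed if the change is made after approval. It needs no new visits, instruments or analyses. A few participants may end on a lower dose, which slightly limits what the study learns about the highest tolerable dose. Possibly one more participant may discontinue, with the withdrawal risk that tapering carries. One of 15 is 1/15 = 6.7%, or one of the 15 − 10 = 5 losses that 16.1 allows while still keeping ten completers.
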